9. SAFETY

During the entire duration of the study, all adverse events (AE) and all serious adverse events (SAEs) are collected, fully investigated and documented in source documents and case report forms (CRF). Study duration encompassed the time from when the participant signs the informed consent until the last protocol-specific procedure has been completed, including a safety follow-up period.

9.1.1 Definition and assessment of (serious) adverse events and other safety related events

An **Adverse Event (AE)** is any untoward medical occurrence in a patient or a clinical investigation participant administered a pharmaceutical product and which does not necessarily have a causal relationship with the study procedure. An AE can therefore be any unfavourable and unintended sign (including an abnormal laboratory finding), symptom, or disease temporally associated with the use of a medicinal (investigational) product, whether or not related to the medicinal (investigational) product. [ICH E6 1.2]

A Serious Adverse Event (SAE) is classified as any untoward medical occurrence that:

- · results in death,
- is life-threatening,
- requires in-patient hospitalization or prolongation of existing hospitalisation.
- · results in persistent or significant disability/incapacity, or
- is a congenital anomaly/birth defect.

In addition, important medical events that may not be immediately life-threatening or result in death, or require hospitalisation, but may jeopardise the patient or may require intervention to prevent one of the other outcomes listed above should also usually be considered serious. [ICH E2A]

Examples of such events are intensive treatment in an emergency room or at home for allergic bronchospasm, blood dyscrasias or convulsions that do not result in hospitalisation, or development of drug dependency or drug abuse.

SAEs are followed until resolution or stabilisation. Participants with ongoing SAEs at study termination (including safety visit) will be further followed up until recovery or until stabilisation of the disease after termination.

Assessment of Causality

Both Investigator and Sponsor-investigator make a causality assessment of the event to the test substance, based on the criteria listed in the ICH E2A guidelines:

Relationship	Description					
Definitely	Temporal relationship					
	Improvement after dechallenge*					
	Recurrence after rechallenge					
	(or other proof of drug cause)					
Probably	Temporal relationship					
	Improvement after dechallenge					
	No other cause evident					
Possibly	Temporal relationship					
•	Other cause possible					
Unlikely	Any assessable reaction that does not fulfil the above conditions					
Not related	Causal relationship can be ruled out					
*Improvement after dechallenge only taken into consideration, if applicable to reaction						

9.1.2 Reporting of serious adverse events (SAE) and other safety related events

All SEs are documented in the participants' file and on the SE report form. The project leader shall report any occurring SE to the responsible EC within 7 days. She shall also submit a report which evaluates the relationship between the event reported and the methods of collecting health related personal data or sampling of biological material within that project, furthermore proposals how to proceed with the project. The project leader shall notify the EC within 7 days of any immediate other safety and protective measures, which have to be taken during the conduct of the research project. In

addition, the project leader shall explain the circumstances, which necessitated the safety and protective measures.

Reporting of SAEs

All SAEs must be reported immediately and within a maximum of 24 hours to the Sponsor-Investigator of the study. The Sponsor-Investigator will re-evaluate the SAE and return the form to the site. SAEs resulting in death are reported to the local Ethics Committee (via local Investigator) within 7 days.

Reporting of SUSARs

A SUSAR needs to be reported to the local Ethics Committee (local event via local Investigator) and to Swissmedic for category B and C studies (via Sponsor-Investigator) within 7 days, if the event is fatal, or within 15 days (all other events).

Handling of Pregnancies

Pregnant participants must immediately be withdrawn from the clinical study. Polyol intake is not contraindicated in pregnancy, as this food additive is generally regarded as safe. However, pregnancy might influence our findings

Periodic reporting of safety

An annual safety report is submitted once a year to the local Ethics Committee.

9.1.3 Follow up of Adverse Events

In case of gastrointestinal symptoms, discontinuation of polyol intake will immediately alleviate symptoms. The participant will be told which test substance he/she had taken to avoid future discomfort (deblinding) and will be advised to consult her/his family practitioner.

10. STATISTICAL METHODS

10.1 Hypothesis

In this exploratory pilot study a hypothesis testing is non-applicable. We expect that glycaemic control is ameliorated in obese, non-diabetic (but insulin resistant) patients compared to baseline, which might be explained through favourable alterations in gut microbiota composition. Should we be able to find an effect, this pilot trial might serve as a basis for further studies including more patients

10.2 Determination of Sample Size

In each group we will examine 20 volunteers. This is a pilot trial and findings will serve to plan larger studies in the future. At this moment no power analysis is possible and group size is chosen on the basis of practical considerations rather than statistical estimation. However, according to our experience, a sample size of min. 20 subjects in each arm will most likely allow us to detect large differences in parameters (> 50%) between the treatments groups.

10.3 Statistical criteria of termination of trial

N/A.

10.4 Planned Analyses

10.4.1 Datasets to be analysed, analysis populations

In this pilot trial which is purely observational, an analysis per protocol is planned. Drop-outs will be replaced, but baseline data of drop-outs might be included to characterize the baseline population. Baseline values of all three groups will be compared, to rule out any baseline differences. The control group will also be examined twice, and the two time-points should yield similar results. Data from each participant before and after treatment will be analyzed in the sweetener groups. In that way, each participant will serve as his or her own control. Post-treatment values of both treatment groups will then be compared to the control group (without treatment).

In case both sweeteners should have an effect on our endpoints, we might combine the two arms for an additional analysis comparing "no sweetener" (n= 20) vs. "sweetener" (n= 40).

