5. STUDY DESIGN

5.1 General study design and justification of design

This pilot trial is a randomized, controlled interventional study; the project set-up will be single-centre, national. Participants will be randomized to one of the three groups: control-group (1), xylitol group (2) or erythritol group (3). They will then get pre-portioned sticks of either xylitol (24g/d; 3x8g) or erythritol (36g/d; 3x12g) or no food supplement (control-group). During the whole period patients will keep a food diary, where they will also report intake of sweeteners and once a week they will fill in a clinical gastrointestinal symptoms questionnaire. The food diary and gastrointestinal symptoms questionnaire will be sent to the clinical trial unit once a week. Once every week volunteers will receive a phone call by the study nurse in order to make sure the sweetener is well-tolerated, compliance is guaranteed and no adverse events occur. At baseline and after 7 weeks, patients will be examined: a) metabolic work-up: oral glucose tolerance test, liver enzymes, blood lipids, b) biomarkers of gastrointestinal permeability and inflammatory response, c) urine and faecal samples (metabolomics), and d) faecal sampling (gut microbiota composition). Upon conclusion of the study, remaining sweetener sticks and questionnaires are returned.

Demographic and personal data (year of birth, weight, height, age, gender, abdominal circumference, blood pressure, medical history) will be saved in a computer database.

Participant recruitment will be achieved through referring physicians from the Ernährungszentrum St. Claraspital, where morbidly obese patients are seen in an outpatient setting before bariatric surgery and are usually on a rather long waiting list before surgery. In case patients are interested in participating,

Effect of the natural sweeteners erythritol and xylitol on vascular function in obese volunteers:

A pilot study, Version 1, 11.4.2016, Version 2, 6.6.2016, Version 3, 25.9.2017

they will be contacted by the principal investigator ([name] [name]) or the study nurse ([name]) and a screening appointment will be made.

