7.4 Compliance with study intervention

Compliance is of uttermost importance in this project. To improve adherence to the intervention, participants are contacted by phone once a week by the study personnel. Apart from answering upcoming questions this allows the study personnel to remind the participant to take the sweeteners regularly, to fill in the questionnaires and to come to the appointments. At the end of the study, the return of unused portions will allow us to estimated compliance. Non-compliance: In case a participant does not take the sweeteners as planned, or fails to fill in the forms and come to the appointments the participant has to be excluded.

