7.5 Data Collection and Follow-up for withdrawn participants

In case a participant wishes to discontinue study participation, the data collected to this time point is included in the analysis. A follow-up visit is not planned in this case.

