Gastrointestinal symptoms will be assessed by use of a validated questionnaire (Clinical rating scale for gastrointestinal symptoms: Svedlund et al., 21). The questionnaire will be used at baseline and at the end of week 3 and 7 (self-reporting). A license agreement will be sent to AstraZeneca (ASTRAZENECA AB, 556011-7482 S-151 85 Södertälje, Sweden). The GSRS is a disease-specific instrument, developed based on reviews of gastrointestinal symptoms and clinical experience, to evaluate common symptoms of gastrointestinal disorders. ^{21,23} The GSRS contains 15 items, each rated on a seven-point Likert scale from no discomfort to very severe discomfort. Based on a factor analysis, the 15 GSRS items break down into the following five scales: abdominal pain (abdominal pain, hunger pains and nausea); reflux syndrome (heartburn and acid regurgitation), diarrhoea syndrome (diarrhoea, loose stools and urgent need for defecation), indigestion syndrome (borborygmus, abdominal distension, eructation and increased flatus) and constipation syndrome (constipation, hard stools and feeling of incomplete evacuation).²³ The scores are calculated by taking the mean of the items completed within an individual scale, with higher scores indicating greater severity of symptoms. The GSRS in European patient populations has a good internal consistency reliability and acceptable construct validity and responsiveness.²³⁻²⁵ The GSRS can be administered in either self-report or interview format.

Intestinal Glucoseabsorption: We will assess intestinal glucose absorption by use of a validated technique ^{26,27}. During the oral glucose tolerance test, 3g of 3-O-Methyl-Glucose (3-OMG) is ingested. 3-OMG is then measured in the plasma samples obtained at 0-30-60-90-120min by means of high performance exchange chromatography.

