8.2.5 Assessments in participants who prematurely stop the study

Participants who discontinue the study are not seen for a follow up visit, as the data obtained after discontinuation will not be useful for our analysis. However, the baseline data will be included in our analyses.

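### Per protocol is the only analysis set, and sweetener drop-outs are replaced and not followed, so the glycaemic comparison with control is made in sweetener completers and does not preserve randomisation

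*Protocol*

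**What the plan says.** - **Analysis set.** Section 10.4.1 names one population: "In this pilot trial which is purely observational, an analysis per protocol is planned. Drop-outs will be replaced". Baseline data of drop-outs may be kept to describe the population. The same section then compares post-treatment values of the two sweetener arms with control, and 10.4.2 sets P < 0.05.
- **Design.** Section 5.1 says: "This pilot trial is a randomized, controlled interventional study".
- **Removal.** Under 7.4 a participant who departs from the intake plan, or who "fails to fill in the forms and come to the appointments the participant has to be excluded". Section 6.4 lists non-compliance and intolerable gastrointestinal effects as reasons for which exclusion may be needed, alongside antibiotics and other adverse events. Section 7.3 ends participation when the polyol is poorly tolerated.
- **Follow-up.** Sections 7.5 and 8.2.5 plan no visit after discontinuation. Section 8.2.5 gives the reason: "as the data obtained after discontinuation will not be useful for our analysis".
- **Use of drop-out data.** Section 6.4 uses what was already collected unless the person objects, and 7.5 says "the data collected to this time point is included in the analysis". Sections 8.2.5, 10.4.1 and 10.5 speak mainly of baseline values. Sections 10.4.1 and 10.5 both replace drop-outs.
- **Tolerability.** Section 4.4 defines the gastrointestinal safety outcome by the symptom questionnaire (GSRS). On timing, 5.1 says "once a week they will fill in a clinical gastrointestinal symptoms questionnaire", whereas 8.2.2 says "The questionnaire will be used at baseline and at the end of week 3 and 7 (self-reporting"; section 4.2 and the schedule agree with 8.2.2.

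**The concern.** Randomisation makes the three arms comparable when they are formed. The plan then removes people for reasons that come after randomisation, and two of those reasons, not taking the sweetener and not tolerating it, cannot apply to controls, who receive nothing. Replacing the removed participants restores 20 per arm but not comparability, because a replacement is counted only by completing.

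Describing the trial as observational does not justify this; it contradicts the design the trial actually has. The loss would also be permanent. A later analysis plan could change the analysis set, but it could not recover final glucose tolerance tests that were never done.

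The pilot is meant to inform larger trials (10.2). Those need drop-out, tolerability and an effect estimate that reflects everyone assigned, and this scheme loses the outcome data of the people who would inform all three.

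**Working it through.** **1. What the plan's own figure supports.** Section 10.2 gives 20 per arm on practical grounds and says differences above 50% should be detectable. No SD, power or drop-out rate is stated, so the figure cannot be reproduced. For scale, with two-sided alpha 0.05 and 80% power, 20 per arm detects (1.960 + 0.842) × √(2/20) = 0.89 SD. A 50% difference then requires a coefficient of variation of at most 0.5/0.886 = 0.56.

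**2. Who can contribute to the primary comparison.** The glucose tolerance test is done at baseline and at about day 49 plus up to 3 days (8.2.1). A participant who stops has no later visit. Last observation carried forward in 10.5 is for single missing blood values. No drop-out therefore contributes to the before-after or between-arm glycaemic comparison.

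**3. How many are missing.** With an assumed drop-out q in a sweetener arm, 20 completers need 20/(1 − q) randomised. That is 22.2, 25.0 and 28.6 at q = 10%, 20% and 30%, or 23, 25 and 29 in whole participants. About 2 to 9 randomised participants per sweetener arm would be outside the comparison.

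**4. Size of the bias, simple form.** The completer mean differs from the all-randomised mean by the fraction removed times the completer-minus-removed difference. Assuming 15-25% removed and a difference of 0.5-1.0 SD:

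- 0.15 × 0.5 = 0.075 SD; 0.15 × 1.0 = 0.15 SD
- 0.25 × 0.5 = 0.125 SD; 0.25 × 1.0 = 0.25 SD

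The standard error of a two-arm difference is √(2/20) = 0.316 SD.

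**5. Size of the bias, selection model.** Let ρ be the correlation between the tendency to stop and an unfavourable outcome. The bias is ρ × φ(z)/(1 − q), where φ is the standard normal density and z its (1 − q) quantile. For q = 20% and ρ = 0.3: 0.3 × 0.280/0.80 = 0.105 SD. The bracketed figures are simulated rejection rates of a nominal 5% two-sample t-test with no true effect. Each uses 20,000 runs of 20 replaced completers against 20 controls with no selection.

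| Drop-out | ρ = 0.2 | ρ = 0.3 | ρ = 0.5 |
|---|---|---|---|
| 10% | 0.039 SD (5.1%) | 0.058 SD (5.6%) | 0.097 SD (5.9%) |
| 20% | 0.070 SD (5.2%) | 0.105 SD (6.1%) | 0.175 SD (9.0%) |
| 30% | 0.099 SD (5.8%) | 0.149 SD (7.4%) | 0.248 SD (12.0%) |

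The sign of ρ is an assumption; reversing it reverses the bias.

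**6. Tolerability.** Suppose 3 of 20 in an arm (15%) stop for diarrhoea before the end of week 3. Under the week 3 and 7 schedule they have no on-treatment questionnaire score, so that 15% adds nothing to the on-treatment questionnaire data. Under the weekly schedule in 5.1 they would have a score from any week completed before stopping. In both cases they should appear as adverse events, because section 9 collects these from consent onwards and 10.4.5 compares them by group without limiting the population.

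**The case against.** The strongest defence is that this is an exploratory pilot. Section 10.1 says hypothesis testing does not apply, and an estimate of what the sweetener does when actually taken is a legitimate question. That supports per protocol as one analysis. It does not support it as the only one, since the plan still compares arms with control at P < 0.05.

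A second point is that no passage shows that people who stop would have had worse glycaemia. This stands. A reader might infer that the bias favours the sweeteners; that is plausible, but the protocol does not establish it. All the shifts calculated above are below one standard error, and they are small at low drop-out. In the paired before-after test, stable differences between those who stop and those who complete cancel. They do not cancel in the post-treatment comparison with control.

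Third, a reader might infer that safety as a whole is assessed only in completers, or that gastrointestinal incidence must be underestimated. The documents do not support this: adverse events are collected and compared for everyone, and participants are telephoned weekly. The gap is limited to the questionnaire measure, which is nevertheless how 4.4 defines the outcome.

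Fourth, the control arm is not unselected. Missed forms and appointments (7.4), antibiotics and other adverse events (6.4), and pregnancy (9.1.2) can remove controls too.

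Finally, the conflict over drop-out data has little effect on the primary endpoint, where data up to discontinuation are baseline data. It matters for measures taken during treatment, such as the questionnaire.

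**Conclusion.** The point holds for the glycaemic comparison. Exclusion or discontinuation, no follow-up, replacement and a single per-protocol set are all stated in the text. Together they mean that sweetener completers are compared with a less selected control arm. The stated justification contradicts the trial's own design.

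The direction and size of the bias are unknown. Under assumed drop-out of 10-30% and correlations of 0.2-0.5 it is about 0.04-0.25 SD against a standard error of 0.32 SD, and the false-positive rate runs from about 5% to 12%. The upper end needs both high drop-out and a strong link between stopping and outcome. The protocol gives no expected drop-out, so neither end can be ruled out.

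Two inconsistencies come with it: 6.4 and 7.5 against 8.2.5, 10.4.1 and 10.5 on the use of drop-out data, and 5.1 against 4.2, 8.2.2 and the schedule on questionnaire frequency. For tolerability the finding is confined to questionnaire scores of people who stop before week 3.

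**What to change.** - **10.4.1:** Remove the description of the trial as observational. Make the primary set all randomised participants in their assigned arm, with per protocol as supportive. Replacements may be recruited but must not stand in for drop-outs in that set. Report drop-outs and reasons by arm, with all randomised as denominator.
- **6.4, 7.4, 7.5, 8.2.5 and 10.5:** Amend together so that stopping the sweetener or missing forms does not end data collection. Invite these participants to the planned final-visit assessments where they consent and the visit is feasible. State one rule for the use of drop-out data. No rule on stopping the sweetener or on withdrawal for pregnancy needs to change.
- **10.5:** State how a missing final visit is handled in the all-randomised set.
- **Questionnaire:** Reconcile the frequency in 5.1 with 4.2, 8.2.2 and the schedule. Add one questionnaire at discontinuation. Analyse tolerability in everyone who took at least one portion, with controls as comparator.

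The cost is an amendment, a few extra final visits and one short questionnaire per participant who stops. The all-randomised estimate will be somewhat diluted by non-adherence, and the supportive per-protocol analysis will show by how much.

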	- Intake of proton pump inhibitors (F Pis) on a regular basis - Intake of antibiotics within the last 3 months before inclusion
	- Intake of pro or prebiotics
	- Chronical diseases of the gastrointestinal tract, history of gastrointestinal surgery with
	major changes to the gastrointestinal tract - Substance abuse, alcohol abuse.
	- Substance abuse, accord abuse Inability to follow procedures due to psychological disorders, dementia or insufficient
	knowledge of project language (German).
	Over a period of 7 weeks, volunteers will ingest the natural sweetener xylitol or erythritol
Measurements and	(or no additional sweetener). Once before and after these 7 weeks we will carry out an
procedures:	oral glucose tolerance test, examine faeces and urine (gut microbiota and metabolomics)
	and take blood samples to analyse lipid profile and liver enzymes. Volunteers will fill in
	a food diary and a questionnaire for gastrointestinal symptoms. The whole study will take
	approximately 8 weeks.
Otrode Due doot /	Randomization to the three study arms will be done by a computer based randomization
Study Product /	(excel). The control group will not receive any sweetener.
Intervention:	The two intervention groups will receive either xylitol or erythritol as follows:
	1st week = run-in (adaption week)
	- 2 days 1 *portion per day (1-0-0)
	- 3 days 2 portions per day (1-1-0)
	- 2 days 3 portions /day (1-1-1)
	2nd to 7th week: Over four weeks the volunteers will ingest 3 portions/day.
	*1 portion xylitol = 8g, 1 portion erythritol = 12g
Control Intervention	We will compare
	a) Baseline findings to post treatment findings. In this way each volunteer will serve as
	his/her own control.
	b) A control group will show whether findings are stable within a participant over 7 weeks.
Number of	In total will enrol 60 volunteers, of which 20 will be controls, 20 will be treated with xylitol
Participants with	and 20 erythritol. This is a pilot trial and a power analysis is not possible. However, we
Rationale:	assume that a relevant difference between the treatments should be observed in 20
-	subjects in each group.
Study Duration:	We plan to carry out this trial within approximately 1 year, starting in August 2016 till
	October 2018, depending on recruitment.
Study Schedule:	Month Year of First-Participant-In (planned): 1st August, 2016
Investigates/a	Month Year of Last-Participant-Out (planned): 1st October, 2018
Investigator(s):	[name] [name]

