10.4.2 Primary Analysis

Descriptive statistics will be used for demographic variables, such as age, weight, height and BMI. Hormone and glucose profiles will be analyzed by calculating the area under the concentration-time curve (AUC) from baseline values. The parameters will be tested for normality by the Shapiro-Wilk test method. One-way ANOVA will be applied to describe differences between the groups. Student's paired t-test will be used to test for significant differences between subjects before and after sweetener intake. All statistical analysis will be done using the statistical software package, SPSS for Windows, Version 22.0 (SPSS Inc., Chicago, USA). Values will be reported as mean \pm SEM. Differences will be considered to be significant when P < 0.05. Statistics will be done by the principal investigator with support of Prof. [name], biostatistician.

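### Baseline equality and control-group stability are to be established with 20 per arm and no criterion except P < 0.05, which cannot support either conclusion

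*Protocol*

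**What the plan says.** Section 10.4.1 gives the baseline comparison of the three arms a purpose and then states an expectation for the controls: "to rule out any baseline differences. The control group will also be examined twice, and the two time-points should yield similar results". The synopsis (Control Intervention, repeated under Statistical Considerations) gives the control group's role as: "A control group will show whether findings are stable within a participant over 7 weeks".

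Section 10.4.2 names the methods. Between arms: "One-way ANOVA will be applied to describe differences between the groups". Within arms: "Student's paired t-test will be used to test for significant differences between subjects before and after sweetener intake". The only decision threshold in the protocol follows: "Differences will be considered to be significant when P < 0.05". Results are to be shown as mean and SEM.

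Section 10.4.1 also plans to compare post-treatment values in both sweetener arms with the control arm. No adjustment for baseline is stated for that comparison.

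On size, section 10.2 says: "In each group we will examine 20 volunteers". It adds that no power analysis was possible.

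**The concern.** Both statements aim at a conclusion of no difference: that the arms start equal, and that the controls do not move. A conclusion of that kind needs a margin, or at least a confidence interval to set against one. The protocol has neither, and leaves undefined what would count as similar or stable. The natural way to apply the plan is to look for P < 0.05 and, on not finding it, to report equality or stability. With 20 per arm that step is unsafe.

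For baseline the aim itself is also misplaced. After proper randomisation, any baseline difference is a chance difference. A test cannot rule it out; adjusting the outcome comparison for the baseline value deals with it.

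The stability statement supports the before-after reading, in which each participant is his or her own control. Section 10.1 words the expected result as improvement relative to baseline. If all arms drift over 7 weeks (through a study effect, a change in diet or regression to the mean) and the drift is missed in the controls, a before-after change in a sweetener arm can be credited to the sweetener.

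**Working it through.** **The plan's own figure.** Section 10.2 expects 20 per arm to detect differences above 50% between groups. It gives no SD and no power, so the figure cannot be reproduced. With an assumed coefficient of variation (CV), two-sample t-test power for a 50% difference is 97% at CV 0.4, 87% at 0.5, 80% at 0.55, 60% at 0.7 and 34% at 1.0. The figure says nothing about showing that a difference is absent.

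**Inputs.** From the protocol: n = 20 per arm, three arms, threshold 0.05, drop-outs replaced. Assumed here: normal outcomes, two-sided tests, effects of 0.3 to 0.8 SD, and, for the controls, a paired t-test.

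**1. Baseline ANOVA.** One arm is shifted by d between-person SDs. The non-centrality is λ = n·d²·(2/3), and the critical value is F(0.95; 2, 57) = 3.16.

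| d | λ | missed |
|---|---|---|
| 0.3 | 1.20 | 85% |
| 0.5 | 3.33 | 66% |
| 0.8 | 8.53 | 28% |

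If the three means are instead evenly spaced over 0.5 SD, the miss rate is 74%. The 95% CI half-width for the difference between two arms is t(0.975, 57)·√(2/20) = 0.63 SD.

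**2. Controls, paired t-test.** With a drift of d SDs of the change, the non-centrality is d·√20 on 19 degrees of freedom.
- d = 0.3: power 0.247, missed 75%.
- d = 0.5: power 0.565, missed 44%.
- The 95% CI half-width is 2.093/√20 = 0.47 SD of the change.

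The two SDs are not the same quantity. If 0.5 refers to the between-person SD, then d = 0.5/√(2(1−r)), where r is the correlation between the two time-points. The control miss rate is then 68% at r = 0, 44% at r = 0.5, 22% at r = 0.7 and 0.3% at r = 0.9.

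**3. Shared drift, no sweetener effect.** Let p be the paired-test power in any one arm. The chance that the controls are non-significant and at least one of two sweetener arms is significant is (1−p)·[1−(1−p)²].
- No drift: p = 0.05; 0.95 × 0.0975 = 0.093, or 9%.
- Drift 0.3 SD of the change: p = 0.247; 0.753 × 0.433 = 0.326, or 33%.
- Drift 0.5 SD of the change: p = 0.565; 0.435 × 0.811 = 0.353, or 35%.

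**4. Does the planned post-treatment comparison catch this?** The scenario in step 3 was simulated with r of 0.5 to 0.8. The false pattern together with a significant three-arm ANOVA on post-treatment values occurs in about 2% of trials, which is 5% to 6% of the trials that show the pattern.

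**5. Does the baseline test screen out imbalance?** In simulated randomised trials, at least one sweetener arm differs from control at baseline by more than 0.3 SD in 54% of trials, and by more than 0.5 SD in 20%. Among trials with a non-significant baseline ANOVA the figures are 51% and 16%. The test changes little; this is chance imbalance at n = 20.

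**The case against.** The strongest reply is that the protocol never says P > 0.05 will be read as equality. The wording for the controls is an expectation, the paired t-test is assigned only to sweetener intake, and the synopsis leaves open what the controls will show. This stands. The P > 0.05 rule is an inference, stronger for baseline (a stated aim of ruling out differences, with a between-group test named) than for the controls, and the control figures describe a test that the protocol does not assign. But if no test applies, the stability statement has no criterion at all, and the same edit is needed.

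A reader might infer that baseline equality and control stability are gates that the effect analyses must pass. The documents do not support that: post-treatment values are compared with control whatever the earlier comparisons show. Because a shared drift cancels between arms, that comparison would usually contradict a false before-after finding (step 4). The 33% to 35% is therefore a risk for the before-after reading, not an error rate for the trial.

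A reader might also take the 51% and 16% in step 5 as harm done by the baseline test. They mostly are not, because the rates with no test are nearly the same. They argue for baseline adjustment.

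Finally, this is an exploratory pilot, section 10.1 disclaims hypothesis testing, and margins may be left to an analysis plan that is not shown. That lowers the stakes. It does not repair a stated aim that the comparison cannot meet, and section 10.2 says the findings will be used to plan larger studies.

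**Conclusion.** The concern holds in limited form. A comparison of 20 per arm cannot rule out baseline differences, and the protocol offers nothing beyond P < 0.05 by which control stability could be judged. If non-significance is taken as equality, the miss rates are 66% for a one-arm baseline shift of 0.5 between-person SD and 44% for a control drift of 0.5 SD of the change. The effect sizes, two-sided testing and the paired test in controls are assumptions made here. The two rates use different SDs and should not be read on one scale.

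The practical harm lies in the within-arm before-after reading, where an undetected shared drift of 0.3 to 0.5 SD of the change raises the false pattern from 9% to 33% to 35% per measure. The between-arm comparison gives partial protection, but without baseline adjustment it carries chance imbalance forward. The logical error depends on none of these figures. The change should be made, though it does not put the trial at risk.

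**What to change.** In section 10.4.1, delete the clause about ruling out baseline differences and drop any baseline significance test. Describe baseline values by arm.

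In section 10.4.1 and the synopsis, replace the similarity and stability wording with text such as:

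> The change in the control group is reported as mean change with 95% CI. A non-significant change is not taken as evidence of stability.

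In sections 10.4.1 and 10.4.2, base the sweetener effect on the difference from control after treatment, adjusted for the baseline value of the same measure (or on the change net of the control change), with 95% CI. Treat the within-arm paired tests as descriptive.

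The cost is a wording amendment and a little extra analysis. The baseline values are already collected, so no new data or participants are needed. The report could no longer say that the arms were equal at baseline or that the controls were stable.
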